## INTRODUCTION

Stroke and traumatic brain injury (TBI) are the most common causes of acquired brain injury, affecting 30000 and 25000 persons in Sweden per year respectively [1, 2]. According to a review article approximately 50 % of patients does not return to work after their stroke [3] and even among patients with the least severe form of TBI, mild TBI, 10-45 % report long-term impairments [4]. This is an indication that a considerable proportion of patients with stroke or TBI does not make a full recovery and live for many years with cognitive, physical and/or emotional impairments.

Earlier studies have found that long-term outcome after both TBI and stroke are determined by a complex combination of injury-related, demographic and neuropsychological factors [3, 5, 6]. This combination is complex enough to avoid revelation of any multivariable prognostic model that can adequately predict patient outcome, despite considerable efforts [6]. Further studies are therefore needed to improve the currently unsatisfactory possibilities of identifying patients at risk of poor outcome.

Previous research suggests that one of the reasons why people suffer differently from what appear to be similar brain injuries has to do with cognitive ability before injury, the so-called cognitive reserve [7]. According to the theory of cognitive reserve, a high premorbid level functions as a cognitive reserve and this leads to the brain network having greater resistance to damage [7]. The protective effect of cognitive reserve is seen in many neurological conditions e.g. Alzheimer's [7]. Common measures of cognitive reserve is education level before injury or measures of crystallized intelligence, so-called hold-tests, i.e. knowledge gained through prior learning, by for instance tests of vocabulary [7, 8].

At a group level, lower performance on cognitive tests indicates a lower probability of returning to work after injury [9] although this is not a consistent finding [10]. Lower education is also associated with lower probability of returning to work after both TBI and stroke [3, 11]. During a neuropsychological assessment it is an accepted fact that the same score on a cognitive test is interpreted differently depending on the individual being assessed. A person with a higher academic degree and an average performance on a language test indicates a disability, while the same performance for someone who has not completed compulsory school indicates a strength. An example of the potent effect education has on neuropsychological tests is that middle-aged people with low levels of education on average perform worse than a group of older, demented patients with higher education [12].

Given that education both seem to impact the susceptibility of the brain to injury and results on neuropsychological tests it is important to take education into consideration when studying the relationship between outcome on neuropsychological tests and return to work after brain injury. In previous studies it is common to control for educational level when investigating the relationship between return to work and results on neuropsychological tests [13, 14] but to our knowledge no-one has looked at whether neuropsychological variables have different significance for work return in different groups based on level of education.

Cognitive reserve is not only related to result on cognitive tests but also to psychological well-being after both TBI and stroke, where higher education is linked to higher life satisfaction and less depression [15, 16]. It would be of interest to investigate whether cognitive reserve interacts with measures of psychological well-being over time and how this is related to more functional measures of outcome after stroke and TBI.

Furthermore higher educational level has been found to be strongly related to better health overall but also to higher health care consumption [17-19]. This apparent contradiction can in part be explained by higher usage of preventive health care services and more use of specialized health care compared to general practitioners among people with higher levels of education [18, 20]. For brain injury, focus of studies of health care usage have frequently been the relationship between health care usage and insurance compensation processes [21, 22]. A better understanding of cognitive reserve influences health service utilization after brain injury, and how this is related to outcome, could be of value in ensuring more equal access to brain injury rehabilitation.

The aim of the current study is to examine the interaction of cognitive reserve with neuropsychological measures, variables related to psychological well-being and variables related to health care usage on long-term outcome after acquired brain injury (TBI or stroke). The study also aims to investigate whether there are differences in levels of fatigue and in health-care consumption based on educational level after stroke or TBI.

## OBJECTIVES

Primary objective is to describe the interaction between measures of cognitive reserve and neuropsychological, psychological and healthcare usage in relation to outcome (i.e work return, satisfaction with life, psychological well-being and overall outcome) after stroke or traumatic brain injury.

Secondary objectives are to describe differences in fatigue related to cognitive reserve after stroke or TBI and to describe differences in health-care usage related to cognitive reserve after stroke or TBI.

## METHOD

### STUDY SETTING

The Brain Injury Rehabilitation Team in Sandviken is the specialized outpatient rehabilitation team for patients of working age with an acquired brain injury in Region Gävleborg. Interviews with the participants was conducted by telephone.

### PATIENT CHARACTERISTICS

Former patients at the Brain Injury Rehabilitation Team in Sandviken, Sweden, who had suffered a stroke or a traumatic brain injury, injury severity ranging from mild to severe according to Glasgow Coma Scale (GCS[26]), between the years 2003-2016 were invited to participate in the study. The study was approved by the Regionala Etikprövningsnämnden Uppsala (2018/242, 2020-05887, 2021-02002). All participants provided written informed consent.

### ELIGIBILITY CRITERIA

The inclusion criteria are 1) Stroke or TBI between the years 2003-2016, 2) Previous or ongoing contact with the outpatient brain injury rehabilitation team in Region Gävleborg, 3) Currently living in Region Gävleborg. Patients with an intellectual disability (IQ>70) or who have acquired a new brain injury will be excluded.

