### OUTCOME VARIABLES

The primary outcome measures are return to work and life satisfaction-Secondary outcomes measures consist of overall outcome after brain injury, a measure of depression, self-rated fatigue and anxiety and health care consumption. Outcome measurements will be assessed during the telephone interview and through collection of health care utilization data. Outcome variables are summarized in table 1.

Table 1: Outcome measures

Outcome measure	Measures
Primary outcome measures	
Return to work	Degree of return to work according to degree of health insurance benefit received by the Swedish Social Insurance Agency
LiSat-11	Life Satisfaction with life overall as well as with specific areas of life. Each area is grade on a scale from 1 to 6 where higher score indicates better satisfaction.
Secondary outcome measures	
GOSE	Overall outcome after brain injury on a scale from 1 to 8, where 1 is death and 8 is upper level of good recovery

HADS	Screening of depression and anxiety, higher scores indicate more severe problems
Fatigue	Fatigue graded according on a VAS-scale by the patients at the time of the telephone interview. 1 is no fatigue, 10 is severe fatigue.
Health care consumption	Number of health care contacts as recorded by administrative systems in Region Gävleborg.

---

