## DATA COLLECTION AND MANAGEMENT

After receiving written consent a structured telephone interview were booked with the patient. The interview followed a standardized manual including questions about employment, overall outcome was assessed with Glasgow Outcome Scale – Extended (GOSE[23]) life satisfaction according to Life Satisfaction Questionnaire (LiSat-11[24]), anxiety and depression according to Hospital and Anxiety Scale (HADS[25]). The interview was approximately 30 minutes and was carried out by a social worker, psychologist or a psychology student with no previous relation to the patient. Information concerning profession, education and level of consciousness according to Glasgow Coma Scale (GCS[26]) or Reaction Level Scale (RLS[27]) at the time of injury where collected from patient charts. Neuropsychological variables (including working memory index, processing speed index, Vocabulary score, Information score, Block Design score, Matrices score and Similarities score from the Wechsler scales [28](Wechsler, 1997)) along with results on HADS and LiSat-11 at the time of admittance to the Brain Injury Team were also collected from patient charts through retrospective chart review. Data of health service utilization, containing information about number and type of contacts with health care services per year and clinic, were collected from the administrative records of Region Gävleborg. Data of health service utilization were collected from three years before injury until four years after injury.

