### STATISTICAL ANALYSIS

Descriptive statistics will be used to depict demographics, injury characteristics, results on neuropsychological tests and psychological screening instruments. Multiple linear and logistic regression will be used in order to detect any interaction effect between measures of cognitive reserve and neuropsychological variables, injury-related variables and variables related to psychological well-being on the outcome variables. Power analysis show that in order to achieve 80 % power, with an alpha-level of 0.05, and three controlling variables in the regression model, the regression analysis require 76 participants.

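### Residence is required only at recruitment, but consumption is counted from one region's records over seven years around injury, so a year lived elsewhere looks like a year without care

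*Combined protocol and SAP*

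**What the plan says.** The relevant statements are spread over five sections of the combined protocol and SAP.

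- **Eligibility Criteria.** The one residence rule is "Currently living in Region Gävleborg". The other link to the region is "Previous or ongoing contact with the outpatient brain injury rehabilitation team in Region Gävleborg", with no date and no minimum. The injury criterion is "Stroke or TBI between the years 2003-2016". Nothing requires the participant to have lived in the region at injury, or in any given year around it.
- **Outcome Variables, Table 1.** Consumption is the "Number of health care contacts as recorded by administrative systems in Region Gävleborg".
- **Data Collection and Management.** The data are numbers and types of contact by year and clinic, and they "were collected from the administrative records of Region Gävleborg". The window is explicit: "Data of health service utilization were collected from three years before injury until four years after injury".
- **Objectives.** One secondary objective is "to describe differences in health-care usage related to cognitive reserve after stroke or TBI". Health care usage is also named in the primary objective, among the variables whose interaction with cognitive reserve is studied.
- **Statistical Analysis.** "Multiple linear and logistic regression will be used in order to detect any interaction effect". The section mentions no person-time, no residence variable and no rule for window years that the regional records do not cover.

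**The concern.** Residence is tested at one date, the time of recruitment. The outcome needs the region's records to cover seven earlier years. The two need not coincide. Someone injured while living elsewhere, who later moved in and was seen by the team, is eligible. So is someone who left after rehabilitation and came back. In both cases care received in another region leaves no entry, and an absent entry adds nothing to a count.

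The error is hard to see in the data. The Data Management section describes range checks, and a low or zero yearly count is a plausible value that would pass them.

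What is at stake is the secondary objective on usage, and usage where it enters the primary interaction objective. The Introduction cites evidence that people with more education use more care. If the more educated had moved more often, undercounting would shrink such a difference; if the less educated had, it would inflate it. The three pre-injury years would also be a poor baseline for anyone who arrived after the injury.

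**Working it through.** **Inputs from the documents.** Window: 3 years before and 4 years after injury, so 3 + 4 = 7 years. Injuries in 2003-2016, so windows run from about 2003 - 3 = 2000 to about 2016 + 4 = 2020. Participants after exclusions (Recruitment): 83 - 3 = 80.

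**Not in the documents.** The share of participants who lived elsewhere during their window, how long for, and whether this differs by education. The shares below are assumptions that show a range. The plan gives no figure of its own on this point to reproduce, and its sample size does not bear on it.

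**Step 1: one participant.** With a constant contact rate, recorded share = (years in window - years away) / years in window. For a participant who moves in two years after injury:

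- post-injury: (4 - 2)/4 = 50% recorded;
- pre-injury: (3 - 3)/3 = 0% recorded.

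**Step 2: post-injury comparison, which is what the secondary objective concerns.** Suppose a share q of one education group lacks 2 of 4 post-injury years, nobody in the other group does, and true use is equal. Recorded ratio of means = 1 - q × 2/4.

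| q (assumed) | recorded ratio | understatement |
|---|---|---|
| 5% | 0.975 | 2.5% |
| 10% | 0.950 | 5.0% |
| 15% | 0.925 | 7.5% |

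If both groups lose the same fraction b of their contacts, the ratio is unchanged. A true difference in means is recorded as (1 - b) times its size, so the undercount weakens it but cannot create one.

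**Step 3: pre-injury years and the pre/post comparison.** Suppose a share q of a group has no regional coverage in all 3 pre-injury years and full coverage afterwards, with constant true use. Pre-injury ratio to a fully covered group = 1 - q. Seven-year ratio = 1 - q × 3/7. Spurious post/pre rate ratio within the group = 1/(1 - q).

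| q (assumed) | pre-injury ratio | seven-year ratio | spurious post/pre ratio |
|---|---|---|---|
| 10% | 0.90 | 0.957 | 1.11 |
| 20% | 0.80 | 0.914 | 1.25 |
| 30% | 0.70 | 0.871 | 1.43 |

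The last column arises whether or not moving is related to education.

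**Step 4: why one seven-year rate is not a sound repair.** Let the true rate after injury be k times the rate before. A participant resident throughout has a pooled rate of (3 + 4k)/7 in units of the pre-injury rate. One who lacks only the pre-injury years has a pooled rate of k. Their ratio is 7k/(3 + 4k), which exceeds 1 whenever k > 1. If use rises after injury, dividing by total resident years would turn an undercount into an overstatement.

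**The case against.** The case on the other side is substantial, and much of it stands.

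- **Zero-counting is not written down.** A reader might infer that the plan sets years lived elsewhere to zero. It does not say so. The data are held by year and clinic, so uncovered years could still be handled apart. What stands is narrower: Table 1 defines a count of regionally recorded contacts, and no rule separates an uncovered year from a year without care.
- **No mover is shown to exist.** Every participant had contact with the regional team and lives in the region now, which makes residence at some time after injury likely. Coverage is therefore probably weaker before injury than after. Leaving and returning matters only if the absence falls within four years of injury. These points limit the risk, but they do not establish residence across the window.
- **A larger headline figure is tempting.** One could say that the participant of Step 1 lacks (3 + 2)/7 = 71% of the window. The secondary objective concerns use after injury, where the loss is 2/4 = 50%. The plan collects the pre-injury years but specifies no baseline analysis for them.
- **The between-group bias may be small next to sampling error.** Assume two groups of 40 and a coefficient of variation of 0.7-1.0 between participants. The standard error of the log ratio of means is then 0.7 × √(2/40) = 0.16 to 1.0 × √(2/40) = 0.22. The bias in Step 2 is -ln(0.975) = 0.025 to -ln(0.925) = 0.078, or about 0.1 to 0.5 standard errors. This stands, under those assumptions, for the post-injury group comparison. It does not answer the pre/post distortion.
- **Address history is not among the data listed**, and collection is described in the past tense. This is a fair point about cost, and the fix allows for it.

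**Conclusion.** The concern holds in a limited form. Residence is fixed only at recruitment, while consumption is taken from one region's records for seven years around injury. Under that definition use is undercounted for anyone not resident throughout. The size for one person follows from the documents: moving in two years after injury removes 2 of 4 post-injury years and all 3 pre-injury years. The size for the study cannot be derived, because the number of movers is not given; the tables above show a range and are not estimates.

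A reader might conclude that the comparison by cognitive reserve is biased. The documents do not support that. It would require moving to differ by education, which they neither report nor rule out. Without such a difference, what remains is undercounting, added noise and a distorted comparison of the periods before and after injury.

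Measurement of the primary outcomes, return to work and LiSat-11, is not affected. Usage does enter the primary interaction objective as a variable, but no effect there has been quantified. The point is worth correcting because the remedy is modest and uses data already held by year.

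**What to change.** Leave eligibility unchanged. For the consumption analyses:

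1. Establish from the chart or regional records in which window years each participant was resident in the region.
2. Treat non-resident years as unobserved, not as zero contacts.
3. Analyse contacts per resident year separately for the pre-injury and post-injury periods, or by year since injury. Do not use one offset pooled over seven years (Step 4). Analysis by year since injury is safer where rates change within a period: the participant who arrives at two years contributes only the third and fourth post-injury years.
4. Add a sensitivity analysis limited to participants resident for the whole period analysed.
5. Report how many participants were not resident throughout, by education group.

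The cost is a residence check for about 80 participants and a short SAP addition. A few participants would contribute fewer years, or drop out of the sensitivity analysis. If log resident years are used as an offset, the SAP must also name a count model, since it now names only linear and logistic regression. Residence history should be added to the listed data and handled under the protocol's own section on amendments. If it cannot be obtained, state the undercount as a limitation of the secondary objective.

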### OUTCOME VARIABLES

The primary outcome measures are return to work and life satisfaction-Secondary outcomes measures consist of overall outcome after brain injury, a measure of depression, self-rated fatigue and anxiety and health care consumption. Outcome measurements will be assessed during the telephone interview and through collection of health care utilization data. Outcome variables are summarized in table 1.

Table 1: Outcome measures

Outcome measure	Measures
Primary outcome measures	
Return to work	Degree of return to work according to degree of health insurance benefit received by the Swedish Social Insurance Agency
LiSat-11	Life Satisfaction with life overall as well as with specific areas of life. Each area is grade on a scale from 1 to 6 where higher score indicates better satisfaction.
Secondary outcome measures	
GOSE	Overall outcome after brain injury on a scale from 1 to 8, where 1 is death and 8 is upper level of good recovery

HADS	Screening of depression and anxiety, higher scores indicate more severe problems
Fatigue	Fatigue graded according on a VAS-scale by the patients at the time of the telephone interview. 1 is no fatigue, 10 is severe fatigue.
Health care consumption	Number of health care contacts as recorded by administrative systems in Region Gävleborg.

---

## SAMPLE SIZE

Multiple linear and logistic regression will be used in the statistical analysis. In order to achieve 80 % power, with a significance level set at  $p < .05$  and 3 prognostic variables, 76 participants are needed to discern medium effects.

## RECRUITMENT

In total 236 patients fulfilled the inclusion criteria and were asked by mail if they wished to participate in the study. Of these 87 accepted and was booked for a telephone interview but only 83 were interviewed, as the remaining 4 was unreachable, in spite of repeated efforts. Chart review of the recruited participants showed that 2 of the recruited participants had an intellectual disability and one had suffered from a new brain injury. These 3 participants were therefore excluded.

## DATA COLLECTION AND MANAGEMENT

After receiving written consent a structured telephone interview were booked with the patient. The interview followed a standardized manual including questions about employment, overall outcome was assessed with Glasgow Outcome Scale – Extended (GOSE[23]) life satisfaction according to Life Satisfaction Questionnaire (LiSat-11[24]), anxiety and depression according to Hospital and Anxiety Scale (HADS[25]). The interview was approximately 30 minutes and was carried out by a social worker, psychologist or a psychology student with no previous relation to the patient. Information concerning profession, education and level of consciousness according to Glasgow Coma Scale (GCS[26]) or Reaction Level Scale (RLS[27]) at the time of injury where collected from patient charts. Neuropsychological variables (including working memory index, processing speed index, Vocabulary score, Information score, Block Design score, Matrices score and Similarities score from the Wechsler scales [28](Wechsler, 1997)) along with results on HADS and LiSat-11 at the time of admittance to the Brain Injury Team were also collected from patient charts through retrospective chart review. Data of health service utilization, containing information about number and type of contacts with health care services per year and clinic, were collected from the administrative records of Region Gävleborg. Data of health service utilization were collected from three years before injury until four years after injury.

## MEASURES

### GLASGOW OUTCOME SCALE-EXTENDED (GOSE)

Glasgow Outcome Scale Extended is a global assessment of functioning after acquired brain injury[23]. It is considered the measure of choice in TBI but is also commonly used after stroke and covers areas of independence, work, social, and leisure activities, and participation in social life [23, 29]. The scale consists of an 8-point ordinal scale divided into upper and lower levels of good recovery (7, 8), moderate disability (5, 6), severe disability (3, 4), vegetative state (2), and death (1).

